1.3.3 ANALYSIS OF ADDITIONAL ENDPOINT(S)

Primary Outcome: the primary outcome measure will be linkage to care or prevention within 3 months of the Aim 1 intervention start. Linkage will be defined for HIV-positive participants as a documented confirmatory HIV test result, and a documented HIV clinic visit following referral. Linkage will be defined for HIV-negative participants as documented evidence of evaluation for PrEP (following standard of care procedures) extracted from medical records.

Secondary outcome: The secondary outcomes will be confirmatory HIV testing uptake 3 – 6 months after intervention start and the initiation of ART, or PrEP (among those screened as eligible), within 3 months of the confirmatory test or eligibility screening. HIV testing uptake will be measured via documented testing records in clinic records and ART start will be measured via documented prescription for ARV medications, and for PrEP start, via oral PrEP prescription.

Third outcome: The third primary outcome is a composite measure meant to capture "success" in HIV prevention and/or treatment behaviors. The measure will be defined as either adequate levels of tenofovir, indicating PrEP adherence (defined as TFV levels of >= 1500 ng/mL in urine indicating adequate adherence vs. < 1500 ng/ml) among HIV seronegative individuals who screened eligible for PrEP or the proportion of HIV-positive participants with viral suppression (defined as HIV RNA <400 c/mL using the Abbott realTime HIV-1 platform and assay, with a detectable threshold of 40 cells per microliter at 6 months. PrEP adherence will be measured at 6 months after initiation using our novel technology of point-of-care rapid testing to assess TFV adherence in urine (developed by Co-I [name] in collaboration with Alere Rapid Diagnostics[™]). For both components of the measure, we will define missing values as failure (i.e. inadequate adherence or unsuppressed).

Analytic Plan: For the test of the *social network-central promoters and small incentive* intervention effect on the primary outcome of linkage to care or prevention within 3 months of intervention start we will utilize a cluster adjusted Pearson's Chi-square test comparing the proportion of subjects with documented linkage to care or prevention in the intervention versus the control arm. In secondary analysis, we will utilize multilevel mixed-effects logistic regression as described in Aim 1 to investigate factors that influence the probability of success of linkage to care and prevention. We will also evaluate the secondary outcomes of ART initiation among HIV-positive persons not currently on treatment, and initiation of PrEP among HIV-negative persons who screen as eligible. We will compare the initiation proportions between study arms using cluster adjusted Chi-square tests and additional multilevel mixed-effects logistic regression to identify influencing factors.

We will measure the combined outcome of 1) Proportion of HIV-positive participants with viral suppression (HIV RNA <400 c/mL) at 6 months missing=failure (unsuppressed) and 2) Proportion of participants adherent to PrEP (TFV levels of >=1500 ng/mL in urine indicating adequate adherence) at 6

months missing=failure (nonadherent). PrEP adherence will be measured at 6 and 12 months after initiation using our novel technology of *point-of-care rapid testing to assess TFV adherence in urine*). (+ about 1 month for all measures)

Secondary Outcomes: HIV testing uptake 3 to 6 months after intervention start and retention on ART at 6 months or PrEP at 6 months. Using clinic records, we will assess whether men had confirmatory HIV testing and those who initiated PrEP and ART attended scheduled appointments and record VL results. (+ about 1 month for all measures)

Analytic approach: We will utilize a cluster adjusted Pearson's Chi-square test comparing the proportion of successes (HIV viral suppression and adequate TFV levels) among men (on ART and PrEP, respectively) in the intervention and control networks. For the outcome of retention on ART or PrEP at 6 months. We will utilize a cluster adjusted Pearson's Chi-square test comparing the proportion of subjects on ART or PrEP at 3 months post trial start who are retained in care at 6 months in intervention versus control group. In secondary analysis, we will utilize Cox proportional hazards regression to investigate factors that influence time to discontinuation of ART or PrEP We will also use multilevel mixed-effects logistic regression to investigate factors that influence the probability of viral suppression and TFV detection in urine. (+ about 1 month for all measures)

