PrEP has the potential to reduce HIV incidence in SSA, but there are many knowledge gaps concerning PrEP implementation, especially in men. Trials have proven the efficacy of PrEP,¹⁰³⁻¹⁰⁸ but varied protection levels have been attributed to low adherence: in trials in young women, adherence was too low to demonstrate effectiveness.^{104,106} PrEP non-use was influenced by partners and peers,^{109,110} and many women perceived themselves to be at low HIV risk. In a trial in discordant couples in which adherence was higher,¹⁰³ only 20% of those at high risk reported they were at risk.¹¹¹ while much has been learned about PrEP adherence among couples and young women, and current interventions (e.g. DREAMS) focus on these populations, much less is known about men's demand for PrEP Our team has implemented PrEP in high-risk populations in the SEARCH trial,^{112,113} and low enrollment (~18%¹¹⁴) supports a need for strategies to stimulate uptake and adherence in this group. Moreover, self-reported adherence has proven limited in PrEP and objective adherence metrics using drug levels measure adherence more accurately.¹¹⁵ This study will fill key knowledge gaps by testing novel strategies to promote PrEP uptake, as well as to measure PrEP adherence among men.

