HIV-negative participants who screen as eligible and enroll in PrEP, and who give their informed consent will provide, in clinic, the urine specimen for measurement of PrEP adherence. The device used for testing is the PUMA Point of Care urine monitoring assay for TFV- Alere. It is not invasive and is merely a testing tool to determine if the patient is taking tenofovir or not at time of a clinic or study visit. Tenofovir is a mainstay of both HIV treatment and prevention and adherence to tenofovir-containing regimens is paramount for efficacy. Given that the effectiveness of PrEP is tightly linked to adherence, a real-time method of measuring tenofovir adherence is desirable. This immunoassay will test for tenofovir detection at a study visit using urine samples. This test is exempt because it is non -invasive (tests tenofovir detection in urine, which is collected noninvasively) and is diagnostic. The study will be working with facilities implementing PrEP (per MOH guidelines) and will work with providers to integrate real-time PrEP adherence monitoring for study participants only. Study participants will be provided PrEP per the MOH guidelines and will come in for their routine visits. At the 6-month -month visit, we will train MOH providers to include the PUMA assay for monitoring adherence. The providers will also administer a brief survey to assess participant adherence to PrEP at the 3-month **and** 6-month visits. As part of boosting

PrEP knowledge, we will use an informational sheet on PrEP available in the local languages, to provide standardized information to participants on PrEP's purpose to prevent HIV acquisition.

Performing and Interpreting Urine Tenofovir Adherence Assay

1. Present patient with a cup and ask them to please provide a urine sample. Of note, there is no need to clean the urethra prior to urine collection. The patient can just urinate into the cup (about 5-10mL). Please ask them to urinate into the pit latrine if they have excess urine after filling the cup to the line.

2. Please ask the patient to screw the lid on to the urine cup after collection and bring it back out to the provider.

3. The provider (using gloves) should use the dropper provided with the urine test to drip 3-4 drops of urine from the urine cup into the divet of the urine test strip (indicated by blue arrow on below picture).

4. After putting the urine drops on the the urine strip test, please lay it on a paper towel and let it develop for 2-3 minutes

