For the primary outcome, we will have \geq 80% power to detect a significant increase in viral suppression and adherence in those on ART and PrEP, respectively, assuming a proportion of successes in the control arm of 70% or greater power (*based on SEARCH trial data on viral suppression rates among fishermen and projected urine TFV detection rates of 70%, weighted for the likely number of men on PrEP (n=168) and men on ART (n=72)*). We assume the observed proportion of successes in the intervention arm will be 89% or greater using an ICC of 0.10, a design effect from clustering of 1.7, and a type-1 error rate of 5%. For the combined primary outcome of retention on ART or PrEP at 6 months (+ about 1 month), this study will have 81% or greater power to detect a significant increase in linkage assuming a proportion retained in care in control arm of 81% (*based on SEARCH data on retention rates weighted for the likely number of men on PrEP (n=168) and ART (n=72)*) if the observed proportion in intervention arm is 96% or greater using the above assumptions.

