## Section 6: Analysis

# 26) Outcome definitions

- a. Primary Outcomes:
  - i. Proportion of HIV testing: The first primary outcome will be the proportion of study participants who self-report HIV testing in the last three months (at the 3 month follow up visit) compared to those who self-report not using testing during the last three months.
  - ii. Proportion of HIV self-testing: The second outcome will be the proportion of study participants who self-report using the self-testing kit in the last three months (at the 3 month follow up visit) compared to those who self-report not using a self-testing kit during the last three months.
  - iii. Proportion with successful linkage to ART or PrEP within 3 months of intervention start (ie: when promoters receive self-test kits to distribute). The second primary outcome will be defined as the proportion of individuals who link to ART (if confirmatory HIV testing is positive) or PrEP evaluation (if confirmatory HIV testing is negative), meaning they present at a study facility/clinic (depending on results of HIV testing) within three months of the intervention start (defined as from when study promotors receive the kits for distribution).
  - iv. HIV treatment and prevention success: The third primary outcome is a composite measure meant to capture "success" in HIV prevention and/or treatment behaviors (ie: Viral suppression among HIV+ and adequate TFV among those prescribed PrEP). The measure will be defined as either adequate levels of tenofovir, indicating PrEP adherence (defined as TFV levels of <1500 ng/mL in urine indicating inadequate adherence vs. ≥ 1500 ng/ml) among HIV seronegative individuals who screened eligible for PrEP *or* the proportion of HIV-positive participants with viral suppression (defined as HIV RNA <400 c/mL using the Abbott realTime HIV-1 platform and assay, with a detectable threshold of 40 cells per microlitre) at 6 and 12 months. Secondary thresholds of <1000 copies/mL will also be examined. PrEP adherence will be measured at 6 and 12 months after initiation using our novel technology of *point-of-care rapid testing to assess TFV adherence in urine* (developed by Co-I [name] in collaboration with Alere Rapid Diagnostics™). For both components of the measure, we will define missing values as failure (i.e. inadequate adherence or unsuppressed).

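### The PrEP denominator of the Aim 3 primary composite is defined three ways, and the stated power fits only men on treatment

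*Protocol*

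**What the plan says.** The composite combines viral suppression in HIV-positive men with adequate urine tenofovir in HIV-negative men. The PrEP half is described in several ways.

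- **Definition.** Protocol 1.3.3 (third outcome) and SAP 26(a)(iv) count tenofovir success "among HIV seronegative individuals who screened eligible for PrEP".
- **SAP gloss.** The same SAP item summarises the outcome as "Viral suppression among HIV+ and adequate TFV among those prescribed PrEP".
- **Analysis.** Protocol 1.3.3 compares successes "among men (on ART and PrEP, respectively) in the intervention and control networks"; SAP 27(c) does the same.
- **Restatement.** The combined outcome is repeated in Protocol 1.3.3 for participants adherent to PrEP, with no denominator given.

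On sampling, Protocol 8.7 says "HIV-negative participants who screen as eligible and enroll in PrEP, and who give their informed consent will provide, in clinic, the urine specimen". It limits specimen collection on the PrEP side to men who start PrEP. Protocol 1.3.3 times the PrEP measurement from initiation. Missing values are failures for both components (Protocol 1.3.3, SAP 26), and SAP 28 applies the same rule to the primary intention-to-treat analysis.

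The Aim 3 power statement (Protocol 1.2, SAP 11) concerns men on ART and PrEP, taken as 72 and 168. It assumes 70% success in control, 89% in intervention, an ICC of 0.10, a design effect of 1.7 and a 5% type-1 error rate.

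**The concern.** Screened eligible, prescribed and on PrEP are three different sets of men. The first differs from the other two by every eligible man who declines. He gives no urine, so under the definition and the missing-data rule he becomes a failure, and under the analysis text he is not counted. PrEP initiation among eligible men is already a secondary outcome, so under the definition he would count once as a non-initiator and again as non-adherent.

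Two analysts following the same documents could therefore report different success rates for a primary outcome, possibly with opposite signs. SAP 27(f) plans no sensitivity analysis that would show both. The control rate, target and power are stated for one of these populations, while the written definition names another.

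**Working it through.** The viral-load half is held fixed at 72 men throughout. Only the PrEP denominator changes.

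**1. The plan's own figure.** Inputs from Protocol 1.2: 168 + 72 = 240 men; p1 = 0.70, p2 = 0.89; design effect 1.7. The test is two-sided at 5% (SAP 16) with 1:1 allocation (Protocol 6.5).

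- Effective n per arm = 120 / 1.7 = 70.6.
- Pooled p = 0.795; √(2 × 0.795 × 0.205) = 0.571; √(0.70 × 0.30 + 0.89 × 0.11) = 0.555.
- z = (0.19 × √70.6 − 1.96 × 0.571) / 0.555 = 0.86, so power = 80.5%.
- In reverse: 70 per arm × 1.7 × 2 = 238 men needed, against 240 assumed.

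The stated power reproduces when the denominator is men on treatment.

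**2. Screened-eligible denominator, decliners as failures.** Let u be the share of eligible men who start PrEP. The documents do not state it, so it is varied. Two readings of the 168 are possible:

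- A: 168 men start PrEP, so 168/u are eligible. Highest possible composite = 240 / (168/u + 72).
- B: 168 men are eligible, so 168u start. Highest possible composite = (168u + 72) / 240.

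Setting the highest possible composite to 0.89:

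- A: 168/u = 240/0.89 − 72 = 197.7, so u = 0.850.
- B: u = (0.89 × 240 − 72) / 168 = 0.843.

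**3. Power with the same uptake in both arms.** Success among treated men stays at 70% and 89%, and the design effect at 1.7.

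| u | Men (A) | Ceiling A | Control v intervention A | Power A | Ceiling B | Control v intervention B | Power B |
|---|---|---|---|---|---|---|---|
| 1.00 | 240 | 100% | 70.0% v 89.0% | 80.5% | 100% | 70.0% v 89.0% | 80.5% |
| 0.95 | 249 | 96.4% | 67.5% v 85.8% | 75% | 96.5% | 67.5% v 85.9% | 74% |
| 0.85 | 270 | 89.0% | 62.3% v 79.2% | 65% | 89.5% | 62.6% v 79.7% | 61% |
| 0.70 | 312 | 76.9% | 53.8% v 68.5% | 53% | 79.0% | 55.3% v 70.3% | 45% |
| 0.50 | 408 | 58.8% | 41.2% v 52.4% | 41% | 65.0% | 45.5% v 57.9% | 31% |

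**4. Power if the intervention raises uptake (reading B).**

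- Uptake 50% v 70%: control 0.70 × (72 + 84)/240 = 45.5%; intervention 0.89 × (72 + 117.6)/240 = 70.3%; power 86%.
- Uptake 40% v 60%: 40.6% v 64.1%; power 80%.

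**5. Possible reversal, PrEP half only, with illustrative rates.** Suppose control uptake is 80% with 70% adherence among starters, and intervention uptake is 60% with 80% adherence. Among men on PrEP the intervention leads, 80% v 70%. Among screened-eligible men it trails: 0.60 × 0.80 = 48% v 0.80 × 0.70 = 56%.

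**The case against.** The best defence is that the intended population is clear and one phrase is out of line. The Protocol abstract, the schedule of activities (3.2), the end-of-study definition (6.10), the specimen cohort (8.7) and the SAP trial design (section 9) all describe men who initiate or are on PrEP. On that reading the 89% describes its own population and the power statement is sound. It can also be said that a man who never starts has no measurement due six months after initiation, so the missing-data rule may cover only samples that were due and not obtained. No text states that decliners are failures.

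This has force, and it rules out saying that the plan definitely counts decliners as failures. It does not remove the conflict. The outlying phrase stands in the formal outcome definition of both documents, where an analyst would look first, and neither document says how decliners are scored.

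A further objection concerns the remedy. Restricting the comparison to men prescribed PrEP conditions on a post-randomisation event that the intervention is meant to change. If it brings in less committed starters, the arms are no longer comparable. Counting non-starters as failures avoids that selection step. This stands, with the qualification that being screened for PrEP is also post-randomisation and is itself the Aim 2 linkage outcome. Neither denominator gives a fully randomised comparison.

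**Conclusion.** The contradiction is real and affects a primary outcome. The stated power of at least 80% belongs to 240 men on treatment and does not carry over to the screened-eligible definition. Under that definition, with decliners as failures, a composite of 89% requires about 84–85% of eligible men to start PrEP even with perfect success among treated men. At the planned 89% success among treated men, any uptake below 100% gives an intervention composite under 89%.

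A reader might go further and infer that the 89% target is out of reach, or that the trial is underpowered for Aim 3. The documents support neither. Uptake among eligible men is not given. The enrolment figure in Protocol 4.2 comes from another study with no stated denominator, so it does not bound uptake here. Nor does a composite below 89% imply lost power: at equal uptake of 50% power is 31–41%, but at 50% v 70% it is 86%. These figures assume equal numbers per arm, a design effect of 1.7 and the plan's success rates among treated men.

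**What to change.** Use one PrEP denominator throughout Protocol 1.3.3 (definition, restatement and analytic approach) and SAP 26 and 27(c), and state how eligible men who do not start PrEP are scored. Settle this before arm-level Aim 3 data are seen.

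- **If the denominator is men with a documented PrEP prescription:** the 70%/89% inputs and the power stand, and decliners count in the initiation outcome. State that the comparison conditions on a post-randomisation event that the intervention targets. Report the screened-eligible version, with non-starters as failures, as a sensitivity analysis in SAP 27(f).
- **If screened eligible is kept:** restate the control rate, target and power for that denominator over a range of assumed uptake, including uptake that differs between arms.

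The cost is wording and a short recalculation. PrEP starts are already taken from prescriptions, and screening and uptake are already in the chart abstraction (SAP 15), so no new data are needed. Keeping screened eligible would lower the stated control rate and target unless uptake is complete.

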1.2 SAMPLE SIZE DETERMINATION AND POWER CALCULATIONS

Aim 1

We calculate that the study will have an 80% or greater power to detect a significant difference in the proportion of HIV testing associated with the intervention arm, assuming a proportion self-testing in the control arm of 38% (observed data from SEARCH in fishermen) if the proportion testing in the intervention arm is 52% or greater (odds ratio of 1.8), calculated using an Intraclass Correlation Coefficient (ICC) of 0.15 (conservative based on SEARCH data), 70 clusters each in the intervention and control arms, average cluster size of 7 in both arms, and a type-1 error rate of 5%.^{125,126} Figure 2 shows statistical power and the range of detectable odds ratios over extremes of clustering effects.

Aim 2

For the Aim 2 combined primary outcome of successful linkage to ART or PrEP within 3 months of intervention start (+about 1 month), this study will have a 80% or greater power to detect a significant increase in successful linkage, assuming a proportion successfully linked at 3 months in the control arm of 24% (based on observed SEARCH trial linkage rates weighted for the number of eligible PrEP HIV-negative men and HIV-positive men not currently in HIV care) if the observed proportion in the intervention arm is 39% or greater (odds ratio of 2.0), using an ICC of 0.15, 70 clusters each in intervention and control arms, a cluster size of 7 in both arms, and a type-1 error rate of 5%. Statistical power for combined ART or PrEP

start is similar, with a reduction in anticipated eligible numbers per cluster reduced to 6 resulting in a small increase in the detectable odds ratio to 2.2 or greater. Power for a separate analysis of ART initiation alone is likely to be low given the small numbers of new HIV infections in the study sample with odds ratios in excess of three or four required.

Aim 3

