#### 10) Randomization

The study will take place in Siaya county, which borders Lake Victoria and has a population of ~1 million. Its subcounties, Rarieda, Bondo, and Alego Usonga, have an estimated 79 beaches and nearly 38,000 fisherfolk. Its population relies heavily on fishing and subsistence farming, and has high rates of poverty. Siaya County is also burdened by high rates of HIV, tuberculosis and malaria. HIV prevalence is 19.5%, 28.9% in those aged 25-49 years, and highest among fisherfolk at 32.1%. High-risk behaviors, including concurrent partnerships, the "jaboya" sex-for-fish economy, and low condom use, enhance HIV risks.

To implement this study, trained RAs will conduct a census of selected beach communities in Siaya. In addition to the census, we will rely on the BMU registries to account for the

possibility that the census omits some fishermen. Using the social network data obtained from the census along with a name matching algorithm, we will identify close male social networks that exist in study communities. " close "networks will typically include 4-10 men. Their defining characteristic will be that individual members of any given network will be connected to each other on multiple domains that indicate strong ties between them. Following the identification of distinct close social networks in communities, we will analyze the network data to determine a *network-central man* having a high degree of connectedness across domains within each network. This man will be considered as the network-central 'promoter' of HIV testing and will be the main individual study staff will contact to implement intervention and control group activities and approached for consent. If a central man is not interested in participation, we will approach the next most central man. Local close networks with consenting promoters will be eligible for randomization.

Close social networks will be randomized 1:1 to intervention and control arms using a computer algorithm that performs randomization stratified by beach and network size in 8 blocks of 2 networks. All network members will receive the study arm condition to which their network is assigned. Participation of all network members is not a requirement for network randomization.

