### Section 4: Statistical Principles

### 16) Level of statistical significance:

Standard levels of significance testing will be used (p=0.05) for two sided-tests. We will report 95% confidence intervals and exact p-values (or p<0.001).

**17)** Description and rationale for any adjustment for multiplicity: (if so, detailing how the type I error is to be controlled.) Our primary outcomes were established in our protocol, and thus no adjustments will be made for multiplicity.

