## **25)** Baseline patient characteristics

We will evaluate several socio-demographic and clinical characteristics at baseline by which we will describe our study sample. These are outlined in Table 1 below. We will stratify these characteristics by intervention and control arms and report median and the inter-quartile range for continuous variables and the N and percent for categorical and dichotomous variables. No significance testing or p-values will be conducted or reported per CONSORT guidelines.

Table 1: Baseline characteristics of Owete participants, by study arm					
Socio-demographic	Age, sex, household size, marital status, polygamous marriage or not, educational attainment, livelihood strategies/ main income sources, household assets, health behaviors and characteristics (general health status, alcohol use, sexual behavior, mental health status).				
Clinical outcomes	HIV status, ART Status, PrEP Status.				
Network structure	(Add in section for characterization of network structures and membership – details to be obtained from [name]).				

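### The Aim 2 linkage outcome has no consistent denominator, and its 24% control rate comes from a narrower group of men than the cluster size it is multiplied by

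*Protocol*

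**What the plan says.** **The test.** Protocol 1.3.3 and SAP 27.b compare arms on linkage within 3 months of intervention start by a cluster-adjusted chi-square test "comparing the proportion of subjects with documented linkage to care or prevention in the intervention versus the control arm". Neither limits who the subjects are. SAP 20.a defines intent-to-treat as those randomised, and SAP 28 scores missing primary outcomes as failure. Protocol 7.1 and 7.2 do not exclude men on ART. In the same part of 1.3.3, the secondary outcome of ART initiation is limited to HIV-positive men not on treatment.

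**Other denominators.** Protocol 3.1 (Known potential risks) says Aim 2 linkage is measured in Aim 1 men who report self-test use. Protocol 6.1 speaks of linkage among men who test, and Table 2 in section 5 of linkage after self-reported testing.

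**The definition.** For HIV-positive men, Protocol 1.3.3 requires a documented confirmatory test and a clinic visit after referral. SAP 26.a.iii glosses linkage more loosely, as presenting at a study facility. Neither says how a man already in care is counted.

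**The power statement.** Protocol 1.2 says "this study will have a 80% or greater power to detect a significant increase in successful linkage". Its inputs are 24% linked among controls and 39% in the intervention arm. The control rate is "weighted for the number of eligible PrEP HIV-negative men and HIV-positive men not currently in HIV care". The calculation uses the same cluster size as Aim 1: 7 in the Protocol, 8 in SAP 11. Only for the later ART/PrEP start outcome is the cluster size cut to 6 for eligibility.

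**Baseline data.** SAP 25 lists "HIV status, ART Status, PrEP Status" among the baseline characteristics.

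**The concern.** A proportion needs a stated denominator, and for this primary outcome the documents offer two.

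If it is all randomised men, it includes men already on ART. As non-linkers they pull both arms' rates down; if their routine attendance counts as linkage, they push both up. Either way the difference between arms shrinks, and a control rate derived for men with something to link to no longer describes the group analysed.

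If it is men who tested or self-tested, the arms are compared within groups selected after randomisation by the behaviour that Aim 1 tries to change. The men who test only because of the intervention may link more or less readily than those who would have tested anyway, so the comparison loses the protection of randomisation. That denominator does not screen out men on ART either.

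At stake are the interpretability of a primary outcome and the agreement between its analysis and its power statement.

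**Working it through.** **Inputs.** Rates of 24% and 39% and ICC 0.15 (Protocol 1.2, SAP 11). "a type-1 error rate of 5" per cent (Protocol 1.2), two-sided: "Standard levels of significance testing will be used (p=0.05) for two sided-tests" (SAP 16). Designs per arm: 40 networks of 8 (SAP 11); 70 of 7 (Protocol 1.2); and 45 of 7, which combines the promoter minimum in Protocol 8.3 with the Protocol's cluster size.

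**Formulas.** Effective n per arm = k·m / [1 + (m − 1)·ICC]. Power = Φ{(d − 1.96·SE₀)/SE₁}, where d is the difference between arms, SE₀ uses the pooled proportion and SE₁ the separate ones.

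**The plan's own figure.**
- 40 × 8: design effect 1 + 7 × 0.15 = 2.05; effective n = 320/2.05 = 156.1. SE₀ = 0.0526, SE₁ = 0.0519; (0.15 − 1.96 × 0.0526)/0.0519 = 0.90; power 82%. This reproduces the SAP statement.
- 70 × 7: design effect 1.90; effective n = 490/1.90 = 257.9; power 96%.
- 45 × 7: effective n = 315/1.90 = 165.8; power 84%.

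**Share on ART (assumption).** The documents do not give it. I take prevalence × treatment coverage. Prevalence is 24–26% in Protocol 4.2, and SAP 10 has it "highest among fisherfolk at 32.1" per cent; coverage is 53–61% (Protocol 4.2).
- Low: 0.24 × 0.53 = 12.7%.
- Protocol high: 0.26 × 0.61 = 15.9%.
- SAP prevalence: 0.321 × 0.61 = 19.6%.

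**Three ways to count these men (share f).**
- Non-linkers: rates 0.24(1 − f) and 0.39(1 − f), so 21% vs 34% at f = 12.7% and 19% vs 31% at f = 19.6%.
- Linked in both arms: rates 0.24(1 − f) + f and 0.39(1 − f) + f, so 34% vs 47% and 39% vs 51%.
- Excluded: rates stay 24% vs 39%; cluster size becomes m(1 − f), so 6.1–5.6 from 7 and 7.0–6.4 from 8.

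| Networks × men, per arm | As stated | Non-linkers | Counted as linked | Excluded |
|---|---|---|---|---|
| 40 × 8 (SAP) | 82% | 74–69% | 66–57% | 79–78% |
| 45 × 7 (promoter minimum) | 84% | 76–72% | 68–60% | 82–80% |
| 70 × 7 (Protocol) | 96% | 92–89% | 86–79% | 95–94% |

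Each range runs from f = 12.7% to f = 19.6%. The last column supposes that 24% applies to the men who remain.

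**The case against.** **The plan never says it counts all men, nor that men on ART are failures.** A reader might infer both and conclude that the linkage test is filled with men who cannot succeed. The first comes only from the unrestricted word for subjects together with the intent-to-treat rule, and Protocol 3.1, 6.1 and Table 2 point elsewhere. The second follows from a strict reading of the definition in 1.3.3 but is not a written rule, and the gloss in SAP 26.a.iii could let routine attendance count. This objection stands, so the defect is an unsettled denominator and the dilution figures are conditional on a reading.

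**The Protocol's power claim is not overturned.** This also stands: at 70 × 7, power stays at 89–92% with men on ART as non-linkers. The shortfall arises in the SAP's 40 × 8, written against Protocol version 4.0 while the supplied Protocol is version 11.0, and in 45 × 7, which no section uses as a power input. But 70 is the upper limit in Protocol 8.3 and 45 the floor.

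**The ART share is assumed.** Its upper end pairs prevalence and coverage from different sources. Protocol 4.2 also says 60% of HIV-positive people need ART; if that means untreated, the share is 0.40 × 24–32.1% = 10–13%, and non-linker power is 76–74% at 40 × 8 and 78–76% at 45 × 7. The size moves but the direction does not.

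**An all-randomised denominator is defensible for a status-neutral intervention.** It is, and it favours neither arm. It would still need a matching control rate and a rule for men in care.

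**Conclusion.** The point holds as an inconsistency in a primary outcome. The denominator is all randomised men under the analysis sections and testers or self-test users under others. Men already in care have no stated classification. The control rate belongs to a narrower group than the cluster size it is applied to. The 39% is a detectable alternative with no source population of its own, so the mismatch concerns the 24%.

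If 13–20% of men are on ART and count as non-linkers, power drops by about 8–13 points at 40 × 8 and at 45 × 7, to below 80%, and by about 4–7 points at 70 × 7, where it stays above 80%. If routine ART attendance counts as linkage, the loss is larger, and at 70 × 7 the range (79–86%) reaches just below 80%. These figures rest on the assumed ART share, ICC 0.15 and a normal approximation. They leave out HIV-negative men who are not PrEP-eligible, whose share is not given and who would dilute the rates further.

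The documents do not support the stronger conclusions that the Protocol's power statement at 70 × 7 is false or that the all-randomised comparison is biased. Bias is a risk of the tester or self-tester denominator.

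**What to change.** 1. In Protocol 1.3.3 and SAP 26.a.iii and 27.b, define the Aim 2 primary denominator as men in randomised networks who are not on ART or PrEP at the baseline survey, regardless of later testing or self-test use. State that men already in care are excluded from it.
2. Report the all-randomised proportion as a sensitivity analysis, with a stated rule for counting men already in care.
3. Bring Protocol 3.1, 6.1 and Table 2 into line with that definition.
4. Restate Aim 2 power with the eligible number per network (about 6 from 7, or 6.4–7 from 8) and one cluster count agreed between Protocol and SAP.

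**Cost.** Wording and a recalculation; no new data, since ART and PrEP status are already listed at baseline. There are three drawbacks:
- The status is presumably self-reported in the survey; clinic abstraction could check it.
- The baseline survey follows randomisation (Protocol 6.6, 8.4), though kits are handed over only after it is complete (SAP 11). Missing baseline status should therefore be tabulated by arm, with a stated rule for men who lack it.
- HIV-negative men who are not PrEP-eligible remain in the denominator, so 24% may still be optimistic and the restated power should show a lower control rate as well.
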